7.2.3. Emergency Unblinding Procedures

In the case of a medical emergency, where knowledge of study drug by the Investigator or an authorized delegate is essential for immediate medical management, a 24-hour code-break service will be available via the IXRS. The date and reason for unblinding are to be documented in the source documents. Any subject for whom the treatment assignment was unblinded is to be discontinued from further study participation. The subject should return for a final study assessment as described in Section 11.9.9.

7.3. Rationale

7.3.1. Rationale for the Study Design

This is a multicenter, randomized, parallel-group, double-blind, placebo-controlled study evaluating the efficacy, safety, and tolerability of SEP-363856 flexibly dosed at 25, 50, or 75 mg/day for 6 weeks followed by 12 weeks of open-label extension of SEP-363856 flexibly-dosed at 25, 50, or 75 mg/day in male and female subjects \geq 55 years of age with a clinical diagnosis of PDP. The collection of safety and efficacy data in an elderly population will further support the development program for SEP-363856, which to date has collected data in adult healthy volunteer subjects and younger adult patients with acute schizophrenia, age 18-40 years. There are no data in a patient population \geq 65 years treated with SEP-363856. The open-label extension will provide additional safety, tolerability and efficacy data of SEP-363856 flexibly dosed at 25, 50, or 75 mg/day for an additional 12 weeks in subjects with a clinical diagnosis of PDP.

7.3.2. Rationale for the Dosages

In the present study, flexible doses of SEP-363856 at 25, 50, or 75 mg/day will be investigated. Selection of this dose range was guided by the following:

- Maximum tolerated dose (MTD) determined for single doses of SEP-363856 administered to healthy adult male subjects in Study SEP361-101 (50 mg)
- Doses administered to healthy adult male subjects (Studies SEP361-103 and SEP361-104) in which SEP-363856 was found to have robust CNS activity (50 mg)
- Study SEP361-104 functional magnetic resonance imaging (fMRI) study in healthy male and female subjects with high or low schizotype characteristics demonstrating effects of SEP-363856 (50 mg) in brain regions such as the orbito-frontal cortex, insula and striatum
- Study SEP361-108 in patients with narcolepsy-cataplexy, suppression of REM sleep at 25 and 50 mg QD demonstrating CNS activity

• In the open-label study SEP361-106 (Part 2) that investigated the PK and efficacy of SEP-363856 at 75 mg/day for 28 days in male and female subjects with schizophrenia, improvement in efficacy measures (PANSS total score, CGI-S) compared with Baseline

Dose selection is further supported by acceptable safety and tolerability data from the 7-day (10 - 75 mg, QD) and open-label 28-day (75 mg, QD) in patients with schizophrenia. Phase 1 studies have also demonstrated dose-proportional increases in plasma SEP-363856 exposure (C_{max}) and AUC).

SEP-363856 has not been administered in patients with PD or PDP prior to this study. The study will therefore start at the lowest dose that showed CNS activity (25 mg).

7.4. Prevention of Missing Data

In an effort to minimize the number of subjects who are terminated from the study prior to study completion, the following study design and conduct elements are implemented:

- Allowance of a dose reduction. Dose reductions to 50 mg/day or 25 mg/day will be allowed by 1 dose level, at any time for reasons of safety and tolerability.
- Allowance of concomitant nonpsychotropic medications during study participation.
- Use of study centers with a good track record of enrolling and following eligible subjects.
- Train the study centers on the importance of continued follow-up and on the informed consent process, ensuring subjects and caregivers understand the commitment they are making, including the intent to complete the trial.
- Monitor data collection at the site level for adherence during the study.

Please see Section 15.3.11 for statistical considerations related to missing data.

8. SELECTION OF SUBJECTS

8.1. Subject Inclusion Criteria

To qualify for participation, subjects must meet all of the following inclusion criteria:

- 1. Subject, caregiver, and/or legally authorized representative understands and is willing to sign informed consent authorizing subject to participate in the study.
- 2. Subject must be willing and able to comply with the study procedures and visit schedules and must be able to follow verbal and written instructions.
- 3. Subject is male or postmenopausal female ≥ 55 years of age.
- 4. Subject meets established diagnostic criteria for Parkinson's disease of at least one year duration, consistent with the UK Brain Bank criteria.
- 5. Subject has psychotic symptoms that began after the diagnosis of PD for at least one month, occurring at least weekly in the month prior to screening (according to subject or caregiver), and severe enough to warrant treatment with antipsychotics.
- 6. Subject has a combined score of at least 6 or an individual score of at least 4 on the Neuropsychiatric Inventory (NPI) Item A (delusions) and/or Item B (hallucinations). This criterion must be met at Visit 1 and Visit 3.
- 7. Subject has a Mini Mental State Examination (MMSE) score > 16 points out of 30.
- 8. Subject has a caregiver (eg, spouse or family member) who will be required to attend all visits and is able to provide study information on various scales such as the NPI.
- 9. Subject is taking antiparkinsonian drugs or deep brain stimulation, with a stable dose/dose regimen and settings for 1 month before screening.
- 10. Female subject must be postmenopausal defined as being amenorrheic for greater than two years with an appropriate clinical profile.
- 11. Male subjects with female partner(s) of childbearing potential must agree to avoid fathering a child and use acceptable methods of birth control from screening until at least 30 days after the last study drug administration.
- 12. Subject is, in the opinion of the Investigator, medically stable based on screening medical history, PE, neurological examination, vital signs, clinical laboratory values (hematology, serum chemistry, urinalysis, lipid panel, coagulation panel, thyroid panel, and serum prolactin).
- 13. Subject has had a stable living arrangement at the time of screening.

8.2. Subject Exclusion Criteria

To qualify for participation, subjects must not meet any of the following exclusion criteria:

1. Subject has psychosis secondary to other toxic or metabolic disorders.

- 2. Subject has atypical Parkinson's disease, Parkinsonism secondary to medication or other neurodegenerative disorders, such as progressive supranuclear palsy or multiple system atrophy.
- 3. Subject has dementia diagnosed concurrent with or before Parkinson's disease, motor symptoms that began less than one year before the onset of dementia or symptoms consistent with the diagnosis of Lewy Body Dementia (DLB), or if the psychosis occurred after ablative stereotaxic surgery.
- 4. Subject failed 2 or more antipsychotic agents given at adequate doses for at least 4 weeks within 1 year before screening. Treatment failure is defined as a complete lack of efficacy. Subjects who had a partial response or who discontinued treatment for reasons of tolerability will be allowed.
- 5. Subject has had a stroke or other uncontrolled serious medical or neurological illness within 6 months of baseline.
- 6. Subject answers "yes" to "Suicidal Ideation" Item 4 (active suicidal ideation with some intent to act, without specific plan) or Item 5 (active suicidal ideation with specific plan and intent) on the C-SSRS at Screening (the past one month) or baseline (ie, since last visit).
- 7. Subject does not tolerate venipuncture or has poor venous access that would cause difficulty for collecting blood samples.
- 8. Subject has participated in an investigational drug study and received investigational drug within 30 days (or longer if the half-life is known to be ≥ 150 hours) prior to the screening visit, or who is currently participating in another interventional study. Observational studies are not exclusionary. Subject has previously received SEP-363856.
- 9. Subject has any clinically significant unstable medical condition or any clinically significant chronic disease that in the opinion of the Investigator, would limit the subject's ability to complete and/or participate in the study.
- 10. Subject has hematological (including deep vein thrombosis) or bleeding disorder, renal, metabolic, endocrine, pulmonary, gastrointestinal, urological, cardiovascular, hepatic, neurologic, or allergic disease that is clinically significant or unstable as judged by the Investigator.
- 11. Subject has a history of malignancy within 5 years prior to the Screening visit, except for adequately treated basal cell or squamous cell skin cancer or in situ cervical cancer. Pituitary tumors of any duration are excluded.
- 12. Subject has, in the opinion of the Investigator, a disorder or history of a condition such as a clinically significant abnormality of the hepatic or renal system or a history of malabsorption, or previous gastrointestinal surgery (eg, cholecystectomy, vagotomy, bowel resection, or any surgical procedure) that may interfere with drug absorption, distribution, metabolism, excretion.
- 13. Subject has known or suspected Alcohol or Substance Use Disorder as defined by DSM-5. The only exceptions are caffeine or nicotine.

- 14. Subject has a clinically significant abnormal 12-lead ECG that may result in the subject's inability to complete the study, as judged by the Investigator.
- 15. Subjects with known human immunodeficiency virus (HIV) seropositivity will be excluded.
- 16. Female subject who is pregnant or lactating.
- 17. Subject has an active and unstable psychiatric disorder as judged by the Investigator.
- 18. Subject is at significant risk of harming him/herself or others according to the Investigator's judgment.
- 19. Subject has attempted suicide within 3 months prior to screening.
- 20. Subject has a history of allergic reaction or suspected sensitivity to any substance that is contained in the study drug formulation.
- 21. Subject has any clinically significant abnormal laboratory values (hematology, serum chemistry, urinalysis, lipid panel, coagulation panel, thyroid panel, serum prolactin, and urine drug screen [Note: Abnormal findings that may be clinically significant or of questionable significance will be discussed with the Medical Monitor prior to including subject.]).
- 22. Subjects with serum alanine transaminase (ALT) or aspartate transaminase (AST) levels ≥ 3 times, serum blood urea nitrogen (BUN) or creatinine ≥ 1.5 X the upper limit of the reference ranges provided by the central laboratory require retesting. If on retesting, the laboratory value remains equal to or above the ULN, the subject will be excluded.
- 23. Subjects with a random (non-fasting) blood glucose at screening \geq 200 mg/dL (11.1 mmol/L) and HbA_{1c} \geq 7% will be excluded.
- 24. Subject has a prolactin concentration > 100 ng/mL at screening or has a history of pituitary adenoma.
- 25. Subject has an abnormal BMI that may result in the subject's inability to complete the study, as judged by the Investigator.
- 26. Subject has experienced significant blood loss (≥ 473 mL) or donated blood within 60 days prior to first dose of study drug; has donated plasma within 72 hours prior to the first dose of study drug or intends to donate plasma or blood or undergo elective surgery during study participation or within 60 days after the last study visit.
- 27. Subject consumes more than 300 mg of caffeine per day (5 cups of coffee or equivalent in caffeinated beverages).
- 28. Subject has used disallowed prescription medications (as described in Section 10.3) within 30 days of screening or anticipates the need for any disallowed medication during their participation in this study.
- 29. Subject is a staff member or the relative of a staff member.
- 30. Subject is in the opinion of the Investigator, unsuitable in any other way to participate in this study.

8.3. Randomization Criteria

To qualify for randomization, subjects must meet all of the following randomization criteria:

- 1. Subject must have a combined score of at least 6 or an individual score of at least 4 on the neuropsychiatric inventory (NPI) Item A (delusions) and/or Item B (hallucinations) at Baseline (Day 1).
- 2. Subject must continue to meet all other inclusion criteria and none of the exclusion criteria at Baseline (Day 1).

8.4. Continuation into Open-label Extension Criteria

To qualify for continuation into the open-label extension period, subjects must meet the following criteria:

- Subject must have completed the 6-week double-blind treatment.
- Subject has not taken any medication other than the study drug for the purpose of controlling PDD symptoms.
- There has been no clinically significant change in the subject's medical condition or Parkinson's disease, in the opinion of the investigator.
- Subject has not answered "yes" to "suicidal ideation" item 4 (active suicidal ideation with some intent to act, without specific plan) or item 5 (active suicidal ideation with specific plan and intent) on the C-SSRS assessment at any time during the DB treatment period.

9. STUDY DRUG MATERIALS AND MANAGEMENT

9.1. Description of Study Drug

Table 6: Investigational Product

Attribute	Investigational Product			
Product name	SEP-363856	SEP-363856	SEP-363856	Placebo
Dosage form	Capsule	Capsule	Capsule	Capsule
Unit dose	25 mg	50 mg	75 mg	NA
Route of administration	Oral	Oral	Oral	Oral
Physical description	Size #0, Swedish Orange Capsule			
Excipients	None	None	None	Microcrystalline cellulose

9.2. Study Drug Packaging and Labeling

9.2.1. Package Description

Study drug will be provided in one-week blister cards containing 9 capsules of SEP-363856 25 mg, 50 mg, or 75 mg, or Placebo capsules (7 days + 2 extra days).

9.2.2. Labeling Description

All packaging for the study drugs will be labeled with:

- Protocol number
- Sponsor's name and address
- Compound/Code or name of investigational drug and dosage form
- Contents (eg, number of capsules)
- Investigational Drug/caution statement
- Instructions for use and storage
- Batch number
- Blank space to record visit number
- Blank space for subject identifiers
- Period of use (as required)
- Unique medication/kit ID number
- Investigator information (if needed)

9.3. Study Drug Storage

All study drug should be stored at United States Pharmacopeia (USP) controlled room temperature 20°C to 25°C (68°F to 77°F); excursions are permitted from 15°C to 30°C (59°F to 86°F).

9.4. Dispensing of Study Drug

An interactive voice/web response system (IXRS) will be used to manage subject screening and randomization. The IXRS is an integrated web-based subject and drug management system.

Study drug blister cards will be assigned by the IXRS based on the treatment schedule and dose adjustment criteria. The IXRS will generate instructions for which study medication unit/number to assign to a subject. Each subject will be dispensed one to four 9-day blister cards per scheduled visit depending on the timing of the next scheduled visit (see Table 2 and Table 3).

Study drug will be taken in-clinic at the Double-blind Baseline visit (Day 1), at Open-label baseline Visit 7 (Day 43; OL Day 1), and on visit days when subject titrates up; with subsequent dosing starting the following day at bedtime. For the remainder of the study, subjects will take one capsule of study drug per day at approximately the same time each evening at bedtime. Study drug may be taken without regard for food.

Study drug should be maintained under the strict control of qualified site staff at all times. Appropriate guidelines should be followed in proper dispensation to the study participant. Proper handling and storage should be followed. IXRS drug dispensing guidelines should be followed for dispensing study drug to the subject, in addition to all accountability records where required. Blister card opening instructions should be reviewed with the subject at time of dispensation. Specific User Manuals will be supplied.

9.5. Study Drug Accountability

The Investigator or designee is responsible for storing the study drug in a secure location and for maintaining adequate records of drug disposition that includes the dates, quantity, and use by subjects. If the study is stopped for any reason or completed, all unused supplies of drug will be returned to the Sponsor, unless other instructions are provided in writing by Sponsor/contract research organization (CRO).

Upon receipt of study drug, the Investigator or designee will inventory the supplies and verify receipt of supplies. The site will perform an acknowledgement of receipt via the IXRS, confirming the date of receipt, inventory and condition of study drug received.

The Investigator or designee will maintain accountability records, including availability of study drug received, and study drug dispensation and return. The Investigator or designee will collect and document the status of all used and unused study drug from study subjects at appropriate study visits per Sponsor's instructions.

9.6. Study Drug Handling and Disposal

Study drug will not be dispensed to any person who is not a study subject under this protocol.

The Investigator or designee is required to return all unused study drug to the Sponsor or designee as instructed. The Investigator or designee is required to maintain copies of study drug shipping receipts, drug accountability records, and records of return or final disposal of the study drug in accordance with local regulatory requirements.

10. TREATMENT OF SUBJECTS

10.1. Study Drug

Active and matched placebo doses (study drug) will be administered QD daily during the double-blind treatment period. Double-blind study drug (active or matched-placebo, as applicable) dosing will be taken in-clinic at Visit 3 (Day 1) and Visit 7 (Day 43; OL Baseline Day 1); as well as on visit days when a subject up-titrates. Subsequent doses starting the following day should be taken at bedtime. For the remainder of the study, subjects will take one capsule of study drug per day at approximately the same time each evening at bedtime.

All study drug doses will consist of capsule(s) containing either SEP-363856 or matched placebo (in order to maintain blinding) administered orally QD.

Subjects may take study drug without regard for food.

Blood samples for determination of plasma SEP-363856 and SEP-363854 concentrations will be collected predose (before study drug administration) and postdose as describe in Table 2 and Table 3 as well as in Section 22. The time and date of the 3 previous doses of study drug, time, and date of sampling must be recorded. The time and date of food intake will be recorded on Day 43 when blood samples are collected for determination of plasma SEP-363856 concentrations.

10.1.1. Dosage Adjustment Criteria

During the DB treatment period:

Subjects randomized to SEP-363856 will receive flexible doses of SEP-363856 (25, 50, or 75 mg/day). Subjects will receive SEP-363856 25 mg/day for 1 week (Days 1 - 7). If there are no safety or tolerability issues, subjects should be up-titrated to 50 mg/day. Subjects still receiving SEP-363856 25 mg/day must have their dose up-titrated to 50 mg/day at Visit 5 (Week 3). At the investigator's discretion, subject may up-titrate to 75 mg during scheduled visits. Up-titration will not be allowed after Visit 6 (Week 5). Dose reductions will be allowed by 1 dose level, at any time for reasons of safety and tolerability. Following a dose reduction, subjects may increase their dose to the next dose level up to Visit 6 (Week 5) at the Investigator's discretion and only during scheduled visits. If safety or tolerability issues result in study medication dose discontinuation or reduction, the Investigator must contact the medical monitor before the subject is re-challenged. The study medication can be re-introduced if agreed on by the Investigator and Medical Monitor.

Subjects randomized to placebo will receive placebo treatment throughout the study.

During the OL extension treatment period:

Subjects will receive flexible doses of SEP-363856 (25, 50, or 75 mg/day). Subjects will receive SEP-363856 25 mg/day for 1 week. If there are no safety or tolerability issues, subjects should be up-titrated to 50 mg/day at Visit 8 (OL Week 2; OL Day 8). Subjects still receiving SEP-363856 25 mg/day must have their dose up-titrated to 50 mg/day at Visit 9 (OL Week 3). At the investigator's discretion, subject may up-titrate to 75 mg during scheduled visits. Dose reductions will be allowed by 1 dose level, at any time for reasons of safety and tolerability. Following a dose reduction, subjects may increase their dose at the Investigator's discretion and

only during scheduled visits. If safety or tolerability issues result in study medication dose discontinuation or reduction, the Investigator must contact the medical monitor before the subject is re-challenged. The study medication can be re-introduced if agreed on by the Investigator and Medical Monitor.

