Subjects will have clinic visits and procedures as outlined in Table 2. Telephone calls to the subjects will be made on the first 2 days after a dose adjustment. An unscheduled visit will be made as early as

possible for dose adjustments or evaluation of safety/tolerability issues. Efforts will be made to ensure that the subject's caregiver remains the same for all study visits. All post-Baseline clinic visits will have a window of ± 2 days relative to the date of the Baseline visit (Visit 3).

Subjects randomized to SEP-363856 will receive flexible doses of SEP-363856 (25, 50, or 75 mg/day). Subjects will receive SEP-363856 25 mg/day for 1 week (Days 1 - 7). If there are no safety or tolerability issues subjects should be up- titrated to 50 mg/day at Visit 4 (Week 2). Subjects still receiving SEP-363856 25 mg/day must have their dose up- titrated to 50 mg/day at Visit 5 (Week 3), unless approved to stay at 25 mg/day by Medical Monitor due to safety and tolerability concerns. At the investigator's discretion, subject may up -titrate to 75 mg during scheduled visits. During the double-blind period, up-titration will not be allowed after Visit 6 (Week 5). Dose reductions to 50 mg/day or 25 mg/day will be allowed by 1 dose level, at any time for reasons of safety and tolerability. During the double-blind period, following a dose reduction, subjects may increase their dose to the next dose level up to Visit 6 (Week 5) at the Investigator's discretion and only during scheduled visits. If safety or tolerability issues result in study dose discontinuation or reduction, the Investigator must contact the Medical Monitor before the subject is rechallenged. The study medication can be re-introduced if agreed to by the Investigator and Medical Monitor.

Dosing Schematic

Notes:

- Dose reduction is allowed at any time for reasons of safety or tolerability; during unscheduled or scheduled visits.
- During the Double-Blind Period, up-titration to a prior dose level is allowed at Investigator's discretion and only during a scheduled visit.
- At Visit 5 (Week 3), the dose should be up titrated to 50mg/day. In the event of tolerability/safety concerns, the dose may remain at 25 mg/day with Medical Monitor approval.
- Visit 6 (Week 5) is the last visit where up-titration can occur during the Double-Blind Period.

Open-label Extension Period:

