Subjects randomized to SEP-363856 will receive flexible doses of SEP-363856 (25, 50, or 75 mg/day). Subjects will receive SEP-363856 25 mg/day for 1 week (Days 1 - 7). If there are no safety or tolerability issues, subjects should be up-titrated to 50 mg/day at Visit 4 (Week 2). Subjects still receiving SEP-363856 25 mg/day must have their dose up-titrated to 50 mg/day at Visit 5 (Week 3), unless approved to stay at 25 mg/day by the Medical Monitor due to safety and tolerability concerns. At the investigator's discretion, subject may up-titrate to 75 mg during scheduled visits. During the double-blind period up-titration will not be allowed after Visit 6 (Week 5). Dose reductions to 50 mg/day or 25 mg/day will be allowed by 1 dose level, at any

time for reasons of safety and tolerability. During the double-blind period, following a dose reduction, subjects may increase their dose to the next dose level up to Visit 6 (Week 5) at the Investigator's discretion and only during scheduled visits. If safety or tolerability issues result in study medication dose discontinuation or reduction, the Investigator must contact the Medical Monitor before the subject is rechallenged. The study medication can be re-introduced if agreed to by the Investigator and Medical Monitor.

Figure 2: Dosing Schematic

Notes:

- Dose reduction is allowed at any time for reasons of safety or tolerability; during unscheduled or scheduled visits.
- During the Double-Blind Period, up-titration to a prior dose level is allowed at Investigator's discretion and only during a scheduled visit.
- At Visit 5 (Week 3), the dose should be up titrated to 50mg/day. In the event of tolerability/safety concerns, the dose may remain at 25 mg/day with Medical Monitor approval.
- Visit 6 (Week 5) is the last visit where up-titration can occur during the Double-Blind Period.

Open-label Extension Period:

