For subjects who complete the DB period and continue into the Open-label (OL) period, the baseline visit for the open-label period will be the end of double-blind treatment period (Week 6 of DB period). Drug will be taken in-clinic on OL Day 1 (Study Day 43) of the open-label period and on study visit days when subject up- titrates; with subsequent dosing starting the following day at bedtime. For the remainder of the study, subjects will take one capsule of study drug per day at approximately the same time each evening at bedtime. After receiving the initial dose of 25 mg (OL Day 1) and after each up-titration, subjects will remain in the clinic for 2 hours of clinical observation; which will include assessments of orthostatic vital signs (1 hour [± 15 min] and 2 hours [± 15 min] post dose); additional medical assessments can be performed as needed per investigator discretion. Findings will be collected on appropriate case report forms (CRFs).

Subjects will be discharged home if medically stable. Dosing will continue once daily (QD) at bedtime for the remainder of the study, without regard for food.

The total daily dose will remain between 25 mg/day and 75 mg/day for the 12-week treatment period. Subjects will receive SEP-363856 25 mg/day for 1 week. If there are no safety or tolerability issues, subjects should be up-titrated to 50 mg/day at Visit 8 (OL Week 2; OL Day 8). Subjects still receiving SEP-363856 25 mg/day must have their dose up- titrated to 50 mg/day at Visit 9 (OL Week 3), however may remain at 25 mg/day due to safety/tolerability issues with medical monitor approval. At the investigator's discretion, subject may up-titrate to 75 mg during scheduled visits.

Dose reductions will be allowed by 1 dose level, at any time for reasons of safety and tolerability. Following a dose reduction, subjects may increase their dose at the Investigator's discretion and only during scheduled visits. If safety or tolerability issues result in study medication dose discontinuation or reduction, the Investigator must contact the medical monitor before the subject is re-challenged. The study medication can be re-introduced if agreed on by the Investigator and Medical Monitor.

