7.2.2. Blinding

During the Double-blind Treatment Period, subjects, Investigator staff, persons performing the assessments, clinical operations personnel, data analysts, and personnel at central laboratories will remain blind to the identity of the treatment from the time of randomization until database lock and unblinding, using the following methods; (1) randomization data are kept strictly confidential until the time of unblinding, and will not be accessible by anyone else involved in the study with the exception of bioanalytical personnel involved in the analysis of PK samples; (2) the identity of the treatments will be concealed by the use of study drugs that are all identical in packaging, labeling, schedule of administration and appearance.

Actual subject identity for plasma concentrations of SEP-363856 and SEP-363854 will not be disclosed before the database lock and the unblinding of the double-blind treatment.

After completion of the DB treatment period, all subjects will receive unblinded flexibly dosed SEP-363856.

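### Protocol 10.1.1 requires the Visit 5 and Visit 9 dose increases without the Medical Monitor exception that the Synopsis and Section 7.1 allow

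*Protocol*

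**What the plan says.** Three parts of the protocol give the titration rule: the Synopsis, Section 7.1 (Overall Study Design) and Section 10.1.1 (Dosage Adjustment Criteria).

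**Visit 5, double-blind.** Section 10.1.1 reads "Subjects still receiving SEP-363856 25 mg/day must have their dose up-titrated to 50 mg/day at Visit 5 (Week 3"), and the sentence ends there. Section 7.1 gives the same increase and adds "unless approved to stay at 25 mg/day by the Medical Monitor due to safety and tolerability concerns". The Synopsis adds "unless approved to stay at 25 mg/day by Medical Monitor due to safety and tolerability concerns". The notes to Figure 2 in 7.1, which also appear under the Synopsis schematic, say "In the event of tolerability/safety concerns, the dose may remain at 25 mg/day with Medical Monitor approval".

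**Visit 9, open-label.** In 10.1.1 subjects still at 25 mg/day "must have their dose up-titrated to 50 mg/day at Visit 9 (OL Week 3). At the investigator's discretion"; the text moves straight to the 75 mg step with no exception between. Section 7.1 gives the increase and continues "however may remain at 25 mg/day due to safety/tolerability issues with medical monitor approval". The Synopsis carries the same exception.

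**The Medical Monitor in 10.1.1.** This role appears there only for re-challenge after a discontinuation or reduction, not for holding a dose.

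**The concern.** The first step up from 25 mg/day is conditional on there being no safety or tolerability issue. Subjects still at 25 mg/day at Visit 5 or Visit 9 are therefore likely to include those held back for such an issue, and for them the sections disagree.

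Three things are at stake.

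- **Safety handling.** Protocol 7.3.2 says the drug has not previously been given to patients with PD or PDP, and 7.3.1 says there are no data at age 65 or over. Section 4.3 reports hypotension and orthostatic hypotension in earlier studies.
- **Consistent conduct.** Two sites with similar subjects could act differently, each relying on the protocol's text.
- **Records.** An approved stay at 25 mg/day complies with 7.1 and departs from 10.1.1. No document says how it would be classed. The per protocol population (Protocol 15.2.2, SAP 5.7) excludes major violations, and SAP 15.1.4.6 repeats the primary model on that population. The modal dose, mean dose and dose-adjustment shift tables in SAP 13 would also reflect whichever rule a site followed.

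**Working it through.** The plan gives no figure to reproduce, so the check compares the texts and then bounds the number of subjects.

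**Step 1: the statements side by side**

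| Place | Visit 5: verb | Visit 5: exception | Visit 9: verb | Visit 9: exception |
|---|---|---|---|---|
| Synopsis, text | must | yes | should | yes |
| Synopsis, schematic notes | should | yes | not covered | not covered |
| 7.1, text | must | yes | must | yes |
| 7.1, Figure 2 notes | should | yes | not covered | not covered |
| 10.1.1 | must | **none** | must | **none** |

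For Visit 5, four statements carry the exception and one does not. For Visit 9, two carry it and one does not. The verb differs between text and notes for Visit 5, and between the Synopsis and 7.1 for Visit 9.

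**Step 2: when the texts lead to different actions.** Take a subject at 25 mg/day at Visit 5 or Visit 9.

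- No safety or tolerability concern: 10.1.1 and 7.1 both call for the increase. No conflict.
- A concern, but no Medical Monitor approval to stay: both still call for the increase. No conflict.
- A concern, with approval to stay: 7.1 and the Synopsis permit the stay; 10.1.1 does not. Conflict.

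**Step 3: whether another sentence in 10.1.1 closes the gap.** It permits a reduction of one dose level for safety or tolerability whenever needed. A reduction follows an increase; it does not permit omitting one. Read literally, 10.1.1 leads to an increase, then a reduction, then Medical Monitor contact before any re-challenge. Section 7.1 leads to a hold. These are different paths.

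**Step 4: ceiling on the number affected.** Protocol 15.1 plans about 24 subjects on SEP-363856 and 12 on placebo.

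- Double-blind: at most about 24 subjects whose actual dose depends on the rule.
- Open-label: everyone restarts at 25 mg/day, so at most about 24 + 12 = 36, reached only if every randomized subject continues.

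The true number needs the share still at 25 mg/day with a concern, which the documents do not give.

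**Step 5: reach into the analysis.** SAP 6.7 compares placebo with all SEP-363856 doses pooled and, apart from some exposure tables, plans no analysis by dose received. The titration rule does not enter the primary model.

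**The case against.** The best defence is that 10.1.1 is a shortened restatement of 7.1. It also omits the visit number for the first double-blind increase, which 7.1 and the Synopsis give. A site that reads 7.1, with its schematic, sees the exception. Safeguards remain in either case: 10.1.1 allows a reduction, and 13.1 requires study drug to stop if the investigator judges that the subject can no longer take part safely. The important-deviation lists in Protocol 15.3.3 and SAP 9 do not name titration.

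Much of this stands. The safeguards limit the consequence, and an effect on deviations is possible rather than shown, since those lists are expressly not exhaustive. But the defence does not remove the contradiction. No text says that 7.1 governs, and 10.1.1 does not refer back to it.

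Four stronger inferences are tempting but not supported:

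- *That 10.1.1 is the controlling section.* No order of precedence is stated. Section 9.4 ties drug assignment by IXRS to dose adjustment criteria but does not cite 10.1.1.
- *That every subject still on the starting dose is affected.* Step 2 above shows that the texts diverge only where there is a safety or tolerability concern.
- *That 10.1.1 keeps placebo subjects on placebo in the extension.* The sentence "Subjects randomized to placebo will receive placebo treatment throughout the study" stands under the double-blind heading, and the open-label paragraph that follows gives SEP-363856. The Synopsis limits placebo to the double-blind period, and 7.2.2 says that afterwards "all subjects will receive unblinded flexibly dosed SEP-363856". This is loose wording only.
- *That the exception must be right because more places state it.* A count of statements does not settle a clinical rule.

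**Conclusion.** The point holds as an internal inconsistency at both visits. Section 10.1.1 states a required increase with no exception; the Synopsis and 7.1 state one, and the schematic notes support them for Visit 5 only. The variation between *must* and *should* adds to the uncertainty. The number affected is unknown, within the ceilings of about 24 and about 36, which assume the planned enrolment and, for the extension, full continuation. The consequences concern conduct, safety handling and the classification of a stay at 25 mg/day. Nothing here invalidates the specification of the primary analysis. It should be corrected because the conflict concerns subjects with a tolerability problem in a population not previously exposed to the drug.

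**What to change.** Reconcile the Synopsis, Section 7.1 with its schematic notes, and Section 10.1.1 so that each visit has one rule, with the same verb and the same statement on whether any exception applies. Which rule applies is for the sponsor to decide. Issue a clarification to sites, and make the deviation review specifications cited in SAP 9 consistent with the outcome so that a stay at 25 mg/day is classed in one way.

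As a minor edit at the same time, word the placebo sentence in 10.1.1 to agree with the Synopsis and 7.2.2.

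The cost is protocol wording and a site communication. No sample size, data collection or primary analysis specification changes.
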